### **Subject Information**

Target accrual: 420. This includes 400 subjects ages 65 and older (over-recruiting by 10% to account for subject drop-out and insufficient cell recovery from biospecimens) and 20 younger subjects (18-40 years of age) as a control group.

Subject population: Potential participants will be identified through routine clinical appointments, advertising with flyers, brochures, an EMR search to identify mail-merge candidates, and existing lists/databases of individuals interested in being contacted about participation in research studies. Subject recruitment and advertisement will occur on Mayo campus and at various sites off campus (e.g., retirement centers). Permission will be obtained from each location before recruitment begins.

#### Inclusion Criteria:

- Male or female adults ages 18-40 or 65 and older at the time of enrollment
- Eligible to receive Fluad® (MF59Flu) or FluZone® (HDFlu) if age 65 or older
- No history of anaphylactic reaction to gelatin, neomycin, or other vaccine component
- Not pregnant
- No immunosuppression or immunodeficiency
- No acute illness at time of vaccination
- Determined by medical history and clinical judgment to be eligible for the study, by being generally healthy, with no autoimmune or immunosuppressive conditions and having stable current medical conditions (subjects with preexisting stable disease, defined as disease not requiring significant change in therapy or hospitalization for worsening disease 12 weeks before receipt of study vaccine, will be eligible. A change in dose or therapy within a category (e.g., change from one nonsteroidal anti-inflammatory drug to another) is allowed. A change to a new therapy category (e.g., surgery or addition of a new pharmacological class) is only allowed if it is not caused by worsening disease. A change to a new therapy category caused by worsening disease is considered significant and therefore ineligible for enrollment.
- Patients with diabetes mellitus are eligible for inclusion if they have had a hemoglobin A1c measurement of <8.0 within the past 6 months prior to enrollment. These hemoglobin A1c measurements are recommended at least twice yearly by the American Diabetes Association (ADA), and the target levels here are representative of the goals of the ADA. These hemoglobin A1c levels will ensure that these participants have good glycemic control. (*American Diabetes Association. American*

*Diabetes Association Position Statement: Standards of Medical Care in Diabetes—2015. Diabetes Care 2015;38(Suppl. 1): S1–S94)*

- Able to follow study procedures in the opinion of the investigator
- Expected to be available for the duration of the study
- Weighs  $\geq 110$  lbs

**Exclusion Criteria:**

- Known or suspected immunodeficiency or receiving treatment with immunosuppressive therapy including cytotoxic agents (e.g., for cancer, HIV, or autoimmune disease).
- Subjects on corticosteroids will be excluded if  $\geq 20$ mg of Prednisone (or equivalent drug) has been (or will be) administered daily for 2 weeks or more. Subjects will be eligible if corticosteroid therapy has been discontinued for at least 30 days.
- Serious chronic medical conditions including metastatic malignancy, severe chronic obstructive pulmonary disease requiring supplemental oxygen, end-stage renal disease with or without dialysis, clinically unstable cardiac disease, or any other disorder that, in the investigator's opinion, precludes the subject from participating in the study. Diabetic patients will be excluded if they do not have a hemoglobin A1c measurement within the past 6 months or if they had a hemoglobin A1c measurement of an A1c  $>8.0$
- Receipt of any blood products, including immunoglobulin, within 6 months of study enrollment.
- Current anticoagulant therapy or a history of bleeding diathesis that would contraindicate intramuscular (IM) injection. (Note: antiplatelet drugs such as aspirin and clopidogrel are permitted.)
- Receipt of any vaccines within the past 30 days prior to enrollment
- Receipt of the current seasonal influenza vaccine other than in this study
- Acute illness within the last 30 days
- Blood donation within the last 56 days prior to study enrollment and within 56 days following the last study visit
- Pregnancy, Nursing or trying to conceive at the time of the study or for 28 days following the baseline visit
- Any condition (e.g. allergic reaction, Guillain-Barre Syndrome) that precludes their receipt of the influenza vaccine
- Currently taking antibiotics to treat a serious infection. Preventative use of antibiotics (i.e. oral surgery) is not an exclusion criterion.
- Diagnosis of a cognitive disorder (e.g. Alzheimer's, Dementia)
- Anemia
- Any medical condition that would, in the opinion of the investigator, interfere with the evaluation of the study objectives

**Visit Schedule for subjects 18-40**

	Baseline Visit - Vaccination
Review of Eligibility/Ineligibility	X

Demographics	X
Study Questionnaire	X
Medication Review	X
Height/Weight	X
Informed Consent	X
Blood Draw – 108ml	X b ,

bFollowing standard practice, subjects will be provided juice, water and cookies after providing their blood sample

### Visit Schedule for subjects 65 and older

	Baseline Visit - Vaccination	Post-Vaccination Visit		
		Day 1	Day 8 (-1 day/+2 days)	Day 28(±3 days)
Review of Eligibility/Ineligibility	X			
Demographics	X			
Study Questionnaire	X			
Medication Review	X	X	X	X
Height	X			
Weight	X	X	X	X
Informed Consent	X			
Blood Draw – 108ml	X b ,			
Blood Draw – 105ml		X b	X b	X b
Flu vaccine	X			
Adverse Events	X	X	X	X

bFollowing standard practice, subjects will be provided juice, water and cookies after providing their blood sample

**Blood will either be collected using a blood collection bag or with tubes. The blood bag collection is the preferred method.**

#### Blood bag collection

- Baseline visit: 108 mL collected in the blood bag. 5 mL will be separated into a redtop tube x1 and 3 mL into an EDTA tube x1
- Day 1 visit: 105 mL collected in the blood bag. 5 mL will be separated into a redtop tube x1
- Day 8 visit: 105 mL collected in the blood bag. 5 mL will be separated into a redtop tube x1
- Day 28 visit: 105 mL collected in the blood bag. 5 mL will be separated into a redtop tube x1

#### Biospecimen tube collection

- Baseline visit: 5 mL redtop tube x1; 10 mL green top sodium heparin tubes x10; 3 mL EDTA tube x1
- Day 1 visit: 5 mL redtop tube x1; 10 mL green top sodium heparin tubes x10
- Day 8 visit: 5 mL redtop tube x1; 10 mL green top sodium heparin tubes x10
- Day 28 visit: 5 mL redtop tube x1; 10 mL green top sodium heparin tubes x10

## Experimental Design:

Below, we briefly describe the assays we will use to monitor/characterize transcriptional changes and specific innate immune response variables at three important time points as informed by other studies and our preliminary data: Baseline (Day 0) and Days 1 and 8 after vaccination. The baseline blood draw allows us to ascertain each subject's pre-existing immune status and provides a baseline upon which to evaluate immunologic changes caused by the vaccine. The Day 1 blood draw allows us to examine early, innate immune responses. The Day 8 sample will be used to characterize plasmablast responses which are directly responsible for humoral immunity and the development of protective Ab titers. The Day 28 blood draw will allow us to examine the peak adaptive immune response.

The assays will be performed either on T- and B-cell depleted PBMCs isolated at each timepoint (for APC immunophenotyping, mRNA, and miRNA) or on T- and B-cell depleted PBMCs stimulated *in vitro* with influenza A/H3N2 (for cytokine/chemokine secretion). This will allow us to capture the *in vivo* and *in vitro* effects of these two vaccines.

**The clinical characterization** of our study subjects will include demographic information, height, weight, medications, and medical conditions that do not meet exclusion criteria. We will also run a CBC to quantify blood leukocyte populations.

**Secreted Cytokine/Chemokine Mediators.** Meso Scale Discovery kits will be used to detect cytokines and chemokines in culture supernatants before and 24 hours after *in vitro* stimulation with influenza A/H3N2.

**Detection of Functional Innate Cell Subsets by Flow Cytometry.** Cellular phenotypes of cells (before and 24 hours after *in vitro* stimulation with influenza virus) will be characterized in Baseline, Day 1, and Day 8 PBMCs by flow cytometry. We will examine the frequency of immune cell types, and characterize their activation by detecting the presence of cell surface markers, co-stimulatory molecules, and activation markers.

**Influenza A/H3N2 Ab Assay.** The HAI Ab assay will be performed using standard protocols. Given the known issues with some A/H3N2 strains, we will utilize influenza antigen matching the vaccine strain and test the antigen for neuraminidase binding to RBCs.

**CMV Serostatus.** CMV Ab titers (IgG) will be measured by multiplex flow-based immunoassay (Bio-Rad).

**B Cell ELISPOT.** Influenza-specific Ab-secreting cells/plasmablasts and memory IgG-like B cells will be quantified in PBMCs using ELISPOTPLUS for Human IgG kits (Mabtech) with (for memory B cells) or without (plasmablasts) R848/IL-2 pre-stimulation.

**mRNA Transcriptomics.** mRNASeq will be performed in Mayo Clinic's Medical Genome Facility on RNA samples extracted from PBMCs harvested at Baseline, Day 1 and Day 8. RNA libraries will be multiplexed with six samples per lane. Flow cells will be sequenced as 51x2 paired-end reads on an Illumina HiSeq. Base-calling will be performed using Illumina's RTA version 1.17.21.3. We will use StringTie,  to process the resulting BAM files and sQTLseeker to evaluate alternately spliced transcripts.

**miRNA Sequencing.** RNA libraries will be prepared with RNA extracted from Baseline, Day 1, and Day 8-harvested PBMCs (NEBNext Multiplex Small RNA Kit, New England Biolabs). Following multiplex adapter ligation (24 samples/lane) and library enrichment by PCR, equimolar amounts of each library will be pooled, purified, and loaded onto flow cells for sequencing (Illumina HiSeq 2000, Illumina cBot and cBot Paired end cluster kit version 3). Bioinformatics analysis will use adapter trimmed reads and miRDeep2.

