## Study Design and Methods

### Methods:

#### Subject Recruitment, Enrollment and Screening

We will screen and recruit 400 generally healthy males and females ages 65 and older who meet all inclusion and exclusion criteria and are willing to receive a flu vaccine.

We will also screen and recruit 20 generally healthy males and females ages 18-40 as a control group. These subjects will only have a baseline blood draw (no flu vaccine administration and no follow-study visits).

Eligible subjects who consent and enroll into the study will undergo a baseline blood draw (up to 108 mL) and then be randomly assigned to receive either the MF59 (Fluad) flu vaccine (N=200) or the High Dose (Fluzone) flu vaccine (N=200). Subjects in the control group will undergo the baseline blood draw only (up to 108 mL). They will NOT receive a flu vaccine. The following sections describe the remaining study visits for the subjects who are ages 65 and older.

Subjects will then be asked to come back for three additional blood draws after their flu vaccination: Day 1, Day 8, and Day 28 after vaccination. Each blood draw will be up to 105mL of blood.

Flu vaccination can occur up to 2 weeks after the baseline blood draw. The Day 1 blood draw will occur the following day after vaccination. The Day 8 blood draw will occur 7-10 days after the vaccination. The Day 28 blood draw will occur 25-31 days after vaccination.

During the Baseline visit we will collect patient demographic information, height, weight, BMI, medication history, medical information, and information on alcohol and smoking use. Patients will also be offered the CDC's influenza vaccine-specific Vaccine Information Sheet that is routinely provided to Mayo patients.

During the 3 follow-up visits we will collect weight, medication history and medical information.

Subjects will be remunerated \$40 for each blood draw visit they complete.

We will also mail subjects, roughly a year after participation, 3 different sleep questionnaires as a way to assess sleep hygiene and immune response.

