### Data Analysis

#### Data Analysis Plan:

The planned analyses for Aims 1 and 2 will follow the same strategies, so for Aim 2 analyses we point out the differences needed to adapt the analyses for Aim 2.

**Aim 2.1 Test the hypotheses that vaccine type (MF59Flu vs HDFlu) or sex is associated with variations in Th cell immune outcomes:** The analysis plans for Aim 1.1 will be followed, but using the Th phenotype and cytokine production outcomes, evaluating change from Baseline to Days 8 and 28.

**Aim 2.2 Test the hypothesis that the expression of specific genes is associated with differences in Th cell immune outcomes:** Analyses will parallel those for Aim 1.2, but use differential Th cell-specific gene and miRNA expression (change from Baseline to Days 8 and 28) as independent variables to evaluate for their association with change in Th cell immune responses.

**Aim 2.3 Test the hypothesis that Th cell transcriptomic signatures mediate the association of vaccine type (or sex) with Th cell immune outcomes:** Analyses will parallel those described in Specific Aim 1.3.

**Aim 2.4 Test the hypothesis that Th cell immune outcomes and transcriptomic signatures from Aim 2.3 will predict markers of humoral immunity (HAI Ab and B cell ELISPOT response):** The analysis plans closely follow the mediation analyses described in Aim 1.4. We will test the hypothesis that Th immune response and their associated genes (Aim 2.3), predict humoral immunity (HAI Ab titer and B cell ELISPOT response) at Day 28. We will also test the hypothesis that additional genes mediate humoral immunity independently of Th responses. To achieve this, we will treat Th responses as adjusting covariates, using the regression model: By adjusting for Th response, we seek genes/genesets that are only associated with humoral immune response.

**Power:** See Specific Aim 1. We anticipate stronger signals in the transcriptomic data from purified CD4+ T cells compared to PBMCs. The increased signal to noise ratio will allow for detection of smaller effects.

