### Potential Limitations and Alternative Strategies for Aims 1 and 2.

False-positive associations will be controlled by our clearly defined analysis plan, the use of false-discovery rates to assess significance, and geneset/pathway analysis to maximize power and minimize false discovery. Statistical power to detect effects is driven by our sample size of 400 subjects, which is larger than most systems biology studies, including our prior study of SDFlu in older subjects where we and others were able to successfully identify transcriptomic signatures of vaccine response. Accumulation of information across multiple genes increases the percent of variability explained by the model and hence increases the likelihood of detecting effects. Our analysis approach will also test the association of each innate and Th cell immune response with the expression of all genes in a specified geneset using kernel methods. Advantages of kernel methods are the following: 1) they allow for correlations among the different genes in a geneset; 2) they are robust to when some genes are positively associated with a response, others are negatively associated with a response, and other genes in the geneset are not associated; 3) and they allow adjustment for covariates. Finally, we will evaluate data-driven genesets using WGCNA to group genes into biological modules, which is an approach we have successfully used (see Preliminary Data).

Separate mediation analyses will be performed for mRNA and miRNA. If we find both mRNA and miRNA to be separate mediators in our initial analyses, we will evaluate their joint effects as a pathway of mediators using techniques developed by VanderWeele. Other confounding factors (e.g., immunosenescence, underlying medical conditions, obesity, and CMV serostatus) will be evaluated in our analyses as potential confounders.

**Expected Results and Impact of Findings for Specific Aims 1 and 2.** Our publications and preliminary data indicate a high likelihood of identifying not only significant vaccine type-

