Transcriptomic Signatures of Influenza Vaccine Responses

NCT03603509

May 19, 2019

Analysis Approach. Subjects will be randomly assigned to vaccine type. For all laboratory assays, randomized complete or incomplete block designs that include technical replicates and laboratory controls will be utilized to ensure sample and assay processing are balanced with respect to collection date, vaccine, and sex, keeping specimens from the same subject adjacent to one another. Data will be scrutinized to identify potential biases, batch effects, or failed assays. We will normalize mRNA-sequence data by Conditional Quantile Normalization (CQN), adjusting for library size, gene length, and GC content. Our primary aim is to test the hypotheses that vaccine type (Fluad vs Fluzone) is associated with the change in immune response as measured by hemagglutination inhibition (HAI) Antibody titer. To test this hypothesis, we will use the Wilcoxon Rank Sum test to test for differences between the vaccine types in the change from baseline HAI to Day 28 HAI Ab titers.

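### If enrolment spans more than one A/H3N2 strain, the unstratified primary HAI test loses power; the SAP should stratify by season and antigen

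*Protocol*

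**What the plan says.** The protocol's Experimental Design section, under the influenza A/H3N2 antibody assay, states: "we will utilize influenza antigen matching the vaccine strain and test the antigen for neuraminidase binding to RBCs". The Exclusion Criteria show that the study vaccine is that season's licensed product. Neither document gives accrual dates, names the A/H3N2 strain, or restricts enrolment to one season.

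The SAP's primary hypothesis is that vaccine type "is associated with the change in immune response as measured by hemagglutination inhibition (HAI) Antibody titer". The test is fixed as follows: "we will use the Wilcoxon Rank Sum test to test for differences between the vaccine types in the change from baseline" to Day 28. No stratum or covariate is mentioned, and the scale of the change (raw titer, fold or log) is not given.

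In the protocol's Data Analysis Plan, Aim 2.4 asks whether Th responses and their associated genes "predict humoral immunity (HAI Ab titer and B cell ELISPOT response) at Day 28". It follows the Aim 1.4 analysis, which is not described in the documents. The section on potential limitations gives examples of confounders to be evaluated; season and antigen are not among them, although the list is only illustrative.

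**The concern.** When the A/H3N2 component changes between seasons, the immunogen and the HAI antigen change together. Subjects from the two seasons then differ in what they were vaccinated with and in what their titers are read against. The pooled test ranks all of these changes on one scale. A between-season difference in the size of the response acts as noise in the vaccine comparison and costs power.

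The analyses relating expression to HAI are not protected by randomisation. If both the HAI response and the expression response differ by season, a gene with no relation to HAI within either season will correlate with HAI in the pooled data.

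Both consequences depend on there being more than one season or strain, which the documents leave open.

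**Working it through.** **Inputs from the documents**
- 400 older subjects, 200 per arm (Protocol, Subject Recruitment, Enrollment and Screening).
- "over-recruiting by 10% to account for subject drop-out and insufficient cell recovery from biospecimens" (Protocol, Subject Information). The evaluable number is not stated. 400 × 0.90 = 360; the other reading, 400 / 1.10, gives about 364. I use 360, or 180 per arm.
- Alpha, power, effect size and SD are not stated. The protocol's power paragraph refers to Specific Aim 1 text that is not in the documents, so there is no planned power figure to reproduce.

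**Assumptions**
- Two-sided alpha of 5% and 80% power when there is no season effect.
- Two seasons of equal size.
- A between-season shift d in mean HAI change, in within-season SD units, shown over a range.

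**Step 1: reference effect.** (1.960 + 0.842) × √(2/180) = 0.295 SD gives 80% power for a difference in means.

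**Step 2: pooled power.** With two equal seasons the pooled variance is 1 + d²/4 times the within-season variance, so

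power = Φ(2.802 / √(1 + d²/4) − 1.960).

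At d = 1: 2.802 / √1.25 = 2.506; Φ(0.546) = 70.7%.

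**Step 3: simulation.** Pooled Wilcoxon against season-stratified Wilcoxon (van Elteren), with simple randomisation, a continuous outcome, 3,000 runs per setting and an effect of 0.295/√0.955 = 0.302 SD. Monte Carlo error is about 0.7 points.

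| d (SD) | Variance factor | Pooled power, formula | Loss (points) | Pooled, simulated | Stratified, simulated |
|---|---|---|---|---|---|
| 0 | 1.000 | 80.0% | 0 | 78.0% | 77.8% |
| 0.25 | 1.016 | 79.4% | 0.6 | 79.3% | 80.0% |
| 0.5 | 1.063 | 77.6% | 2.4 | 78.0% | 79.8% |
| 1.0 | 1.250 | 70.7% | 9.3 | 69.2% | 78.6% |
| 1.5 | 1.563 | 61.1% | 18.9 | 57.6% | 79.5% |

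At d = 1, pooling is equivalent to analysing 360 / 1.25 = 288 subjects. Simulated type I error of the pooled test was 4.7% to 5.2%. If the arms happen to be balanced within season, the pooled test becomes conservative (2.8% at d = 1, 1.3% at d = 1.5). It does not become anti-conservative.

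**Step 4: expression and HAI.** Take a gene unrelated to HAI within season. If HAI shifts by a and expression change by b between two equal seasons (both in SD units), the induced correlation is

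r = (ab/4) / √[(1 + a²/4)(1 + b²/4)].

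Rejection probabilities use Fisher's z with N = 360 and no season term.

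| HAI shift a | Expression shift b | r | P(p < 0.05) | P(p < 0.001) |
|---|---|---|---|---|
| 1.0 | 0 | 0 | 5% | 0.1% |
| 0.5 | 0.5 | 0.06 | 20% | 1.5% |
| 1.0 | 0.5 | 0.11 | 54% | 11% |
| 1.0 | 1.0 | 0.20 | 97% | 71% |

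The first row shows that a shift in HAI alone creates no false association.

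**Step 5: what the stated safeguards reach.** The SAP balances assay processing on collection date, vaccine and sex, keeps a subject's specimens together, and reviews batch effects. Under Aim 2.2 expression enters as change from baseline. These measures limit processing artefacts and cancel additive offsets shared by a subject's samples. Taking the HAI change removes a constant antigen offset only on a log or fold scale. None of these measures removes a strain-specific difference in the size of the response.

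**The case against.** The strongest objection is that the premise is not in the documents. Nothing says enrolment runs over more than one season or that the strain changes; the protocol refers to the vaccine strain in the singular. It also puts the local population aged 65 and over at 30,447 to 54,748, of which 400 is 0.7% to 1.3%, so a single season cannot be ruled out. This stands, and it makes the point conditional.

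Several stronger readings are tempting but unsupported:
- **That the vaccine comparison is biased.** Assignment is random and the type I error is held. Only efficiency is at issue.
- **That power will be lost and false signals reported.** With one season there is no loss, and at a 0.5 SD shift the loss is about 2 points. The larger losses depend on shifts for which the documents give no figure.
- **That the 20% to 97% rejection rates describe what the study would report.** They are for one nominal 5% test. The protocol plans "the use of false-discovery rates to assess significance", without giving a level, and expression enters as a change score. The shift would therefore have to be in the expression response, not in its level or in a shared batch offset.
- **That the sex analyses are confounded by season.** This would require the sex mix to differ between seasons, and nothing suggests that it does.
- **That the gene models omit season.** The Aim 1 models are not in the documents and the confounder list is illustrative, so omission cannot be shown.

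What remains is that the primary test is fully written out without a stratum, the antigen is tied to the season's vaccine, and no text closes the multi-season possibility.

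**Conclusion.** The point holds in conditional form. If enrolment spans seasons with different A/H3N2 components, the planned primary test remains valid but loses power: about 2, 9 and 19 points at between-season shifts of 0.5, 1 and 1.5 SD. These figures assume two equal seasons, 180 evaluable subjects per arm, two-sided 5% and 80% reference power. With one season the loss is zero. False associations between expression and HAI are possible only if the expression change also differs by season and the models leave season out. Their frequency depends entirely on the assumed shifts and on the significance threshold. The change is worth making because it costs almost nothing, and because a stratum chosen after titers are seen would be data-driven.

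**What to change.** In the SAP, replace the pooled Wilcoxon test with a van Elteren rank-sum test of HAI change, stratified by influenza season/HAI antigen. With a single stratum this is the planned test. Add season/antigen as a covariate in the models relating expression or cellular responses to HAI and ELISPOT. State the number of seasons and the A/H3N2 strain or strains, or state that one season and one antigen apply.

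The cost is a few sentences of SAP text. No new data are needed: visits are timed from vaccination, so the vaccination date is held, and the laboratory knows the antigen used. Each extra season takes one degree of freedom in the models. In the simulation with no season shift, stratifying cost nothing measurable (77.8% against 78.0%).
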